
Study Drugs, Doses, and Modes of Administration:
	
During Dose Escalation (Part 1), the patient's weight at screening (baseline) will be used to calculate the initial dose of DS-6157a. On Cycle 1 Day 1, DS-6157a will be infused for 90 ± 10 minutes. A 21-day observation period (Cycle 1) will then occur, at the end of which all relevant safety data will be reviewed. Patients will continue to receive DS-6157a (once every 3 weeks [Q3W]) until progression of disease (PD) according to Response Evaluation Criteria in Solid Tumors (RECIST) v1.1 as assessed by the Investigator, unacceptable toxicity, death, or withdrawal of consent. If there is no infusion-related reaction after the initial 90-minute infusion on Cycle 1 Day 1, the subsequent dose of DS-6157a may be infused for 30 ± 5 minutes based on the clinical judgment of the Investigator and/or Medical Monitor, but this reduced infusion rate is not mandatory.
 
During Dose Expansion (Part 2), on Cycle 1 Day 1 the RDE of DS-6157a will be infused for 90 ± 10 minutes. If there is no infusion-related reaction after the initial 90-minute infusion on Cycle 1 Day 1, the subsequent dose of DS-6157a may be infused for 30 ± 5 minutes based on the clinical judgment of the Investigator and/or Medical Monitor, but this reduced infusion rate is not mandatory. Patients will then continue to receive DS-6157a Q3W, until PD according to RECIST v1.1 as assessed by the Investigator, unacceptable toxicity, death, or withdrawal of consent.
 
As exceptions, patients in both Part 1 and Part 2 may be treated beyond initial radiological progression (according to RECIST v1.1) on a case-by-case basis (with agreement from the Medical Monitor), if the Investigator feels that it is in the patient's best interest, the patient re-consents to continue receiving study treatment in a separate consent form, and as long as the patient is deriving benefit from the treatment and all the following criteria are met:
 
 
• Absence of clinical symptoms or signs indicating clinically significant disease progression
 
• No decline in performance status
 
• Absence of rapid disease progression or threat to vital organs or critical anatomical sites (e.g., CNS metastasis, respiratory failure due to tumor compression, spinal cord compression) requiring urgent alternative medical intervention
 
• No significant, unacceptable or irreversible toxicities related to study treatment
 
• Patient agrees to continue protocol-specified assessments and monitoring
 
 
However, the first evidence of radiographic progression will be captured as the progression event for efficacy assessments in these patients who are allowed continued treatment beyond progression.

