## 5.1 Treatment Plan

DS-6157a will be prepared and administered via intravenous (IV) infusion according to the details in the Pharmacy Manual.

For Dose Escalation (Part 1), on Cycle 1 Day 1 DS-6157a will be infused for  $90 \pm 10$  minutes. A 21-day observation period (Cycle 1) will then occur, at the end of which all relevant safety data will be reviewed. Patients will continue to receive DS-6157a (Q3W) until unacceptable toxicity, progressive disease (PD), death, or withdrawal of consent (Section 3.3). If there is no infusion-related reaction on Cycle 1 Day 1, the subsequent dose of DS-6157a may be infused for  $30 \pm 5$  minutes based on the clinical judgment of the Investigator and/or Medical Monitor, but this reduced infusion rate is not mandatory.

For Dose Expansion (Part 2), on Cycle 1 Day 1 the RDE of DS-6157a will be infused for  $90 \pm 10$  minutes. Patients will then continue to receive DS-6157a (Q3W) until unacceptable toxicity, PD, death, or withdrawal of consent (Section 3.3). If there is no infusion-related reaction after the initial dose, the subsequent dose of DS-6157a may be infused for  $30 \pm 5$  minutes based on the clinical judgment of the Investigator and/or Medical Monitor, but this reduced infusion rate is not mandatory.

For both Dose Escalation and Dose Expansion, the patient's weight at screening (baseline) will be used to calculate the initial dose. The dose will be recalculated if the patient's weight changes by more than 10% from baseline, or per institutional standard even if the weight change is less than  $\pm 10\%$ . This new body weight will be used to calculate the dose for subsequent cycles of DS-6157 infusion.

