### **5.1.3 Maximum-Tolerated Dose**

Once the dose escalation stopping criteria are met, the Sponsor will estimate the MTD using a Bayesian logistic regression model (BLRM) and following the escalation with overdose control (EWOC) principle, where the estimated MTD is the dose with the highest posterior probability of the target DLT rate interval of  $16\% < \text{DLT rate} \leq 33\%$  fulfilling the overdose control constraint, i.e. probability of a DLT rate  $>33\%$  (sum of probabilities for excessive and unacceptable toxicity) should be less than 25%. The final MTD will be decided based on considerations of the estimated MTD and on an overall assessment of safety data from subsequent cycles and PK information collected at all different doses tested.

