## 6. DOSE MODIFICATIONS

If toxicity occurs, the toxicity will be graded using the NCI [CTCAE Version 5.0](#), and appropriate supportive care treatment will be administered to decrease the signs and symptoms thereof. Dose adjustments will be based on the organ system exhibiting the greatest degree of toxicity.

The Investigator will evaluate which toxicities are attributed to the study drug and adjust the dose of the drug as recommended below. All dose modifications must be based on the worst preceding toxicity (CTCAE version 5.0).

Specific criteria for interruption, re-initiation, dose reduction, and/or discontinuation of DS-6157a are listed in [Table 2](#). All interruptions or modifications must be recorded on the AE and drug administration CRFs. Appropriate clinical experts must be consulted as deemed necessary.

There will be no dose modifications for Grade 1 or Grade 2 AEs unless specified below in [Table 2](#). For a recurrent Grade  $\geq 3$  AE, the patient will be permanently discontinued from study treatment based on Investigator discretion.

Prophylactic or supportive treatment for expected toxicities, including management of TEAEs, will be at the treating physician's discretion and per institutional guidelines, except for prophylactic treatment prior to the DLT evaluation period.

*CONFIDENTIAL*

Two dose reductions will be permitted (the dose cannot be reduced to <1.6 mg/kg) in any patient. Once the dose of DS-6157a has been reduced because of toxicity, all subsequent cycles must be administered at that lower dose level unless further dose reduction is required. More than 2 dose reductions are not allowed and the patient will be withdrawn from the study treatment if further toxicity meeting the requirement for dose reduction occurs.

During the dose escalation part of the trial, intra-patient dose escalation (IPDE) of DS-6157a may be allowed on a case by case basis in patients who may benefit from IPDE based on the clinical judgement of the investigator and in agreement with the Medical Monitor and Sponsor. The eligibility criteria for consideration of patients for IPDE are the following:

- Patient must provide consent for IPDE.
- A minimum of 4 cycles of treatment and evaluations must be completed before IPDE
- Patient must meet inclusion criteria of #1-3, 6 and 8 based on the most recent data, and 9 (except for DS-6157 treatment) again. Any criteria that did not meet the eligibility can be re-tested.

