**Table 2 Dose Modifications for DS-6157a**

Worst toxicity CTCAE v5.0 Grade (unless otherwise specified)	Dose or schedule modification for DS-6157a
No toxicity	Maintain dose and schedule
Infusion-Related Reaction	
Grade 1 (Mild transient reaction; infusion interruption not indicated; intervention not indicated)	No interruption or change in the infusion rate is indicated.
Grade 2 (Therapy or infusion interruption indicated but responds promptly to symptomatic treatment (e.g., antihistamines, nonsteroidal anti-inflammatory drugs (NSAIDs), narcotics, IV fluids); prophylactic medications indicated for ≤24 hrs)	
Grade 2 IRR occurring during infusion of DS-6157a:
 
 
Administration of DS-6157a must be interrupted and symptomatic treatment started (e.g. antihistamines, NSAIDs, narcotics, IV fluids).
 
If the event resolves or improves to Grade 1, infusion can be re-started at a 50% reduced infusion rate.
 
 
Grade 2 IRR occurring post infusion of DS-6157a:
 
 
Symptomatic treatment must be started (e.g., antihistamines, antiemetics, NSAIDs, IV fluids) until the event resolves or improves to Grade 1.
 
 
Subsequent administrations of DS-6157a after any Grade 2 IRR occurring during or post infusion of DS-6157a :
 
 
Premedication (e.g., acetaminophen, diphenhydramine, and/or corticosteroids or equivalents) should be considered at the Investigator’s discretion. If the Grade 2 event recurs despite pre-medication, then all subsequent administrations of DS-6157a must be conducted at the 50% reduced infusion rate and/or with pre-medication.
 
If the infusion rate is reduced by 50% (regardless of pre-medication) and the Grade 2 event does not recur at a given cycle, then administrations of DS-6157a at subsequent cycles can be conducted at the initial infusion rate at the investigator’s discretion. If the Grade 2 event recurs at the initial infusion rate, then all subsequent administrations of DS-6157a must be conducted at the 50% reduced infusion rate and with pre-medication.
 

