### **8.1.2 Preparation and Administration of DS-6157a**

The first dose of DS-6157a in each patient will be infused for  $90 \pm 10$  minutes. If there is no infusion-related reaction after the initial dose, the subsequent dose of DS-6157a may be infused for  $30 \pm 5$  minutes based on the clinical judgment of the Investigator and/or Medical Monitor, but this reduced infusion rate is not mandatory.

Preparation and administration instructions will be provided in the pharmacy manual.

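### After a Grade 2 infusion reaction recurs despite pre-medication, Table 2 can be met by repeating the regimen that has just failed, and its 50% rate cut has no named reference rate

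*Combined protocol and SAP*

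**What the plan says.** Two infusion times exist. The first dose runs over 90 ± 10 minutes. Section 5.1 then opens a faster option: "If there is no infusion-related reaction on Cycle 1 Day 1, the subsequent dose of DS-6157a may be infused for" 30 ± 5 minutes. Section 8.1.2 makes this a matter of clinical judgment, "but this reduced infusion rate is not mandatory".

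For infusions after a Grade 2 reaction, Table 2 has two rules.

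- **First rule.** Pre-medication is to be considered, at the investigator's discretion. If the Grade 2 event comes back in spite of it, every later infusion "must be conducted at the 50% reduced infusion rate and/or with pre-medication".
- **Second rule.** If the rate was halved and the event stayed away, "administrations of DS-6157a at subsequent cycles can be conducted at the initial infusion rate", at the investigator's discretion. If the event comes back at that rate, every later infusion "must be conducted at the 50% reduced infusion rate and with pre-medication".

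Table 2 gives no duration for either rate and does not say from which infusion the 50% is taken. A Grade 3 or 4 reaction ends treatment. Section 6 also has a general recurrence rule, under which "the patient will be permanently discontinued from study treatment based on Investigator discretion", but it applies only to Grade 3 or higher.

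**The concern.** The first rule is worded as an obligation, yet *and/or* lets it oblige nothing new. A patient who has reacted twice, the second time under pre-medication, can be given the identical infusion a third time within the protocol. The second rule asks for more, so two sites can read adjacent lines and treat the same recurrence differently.

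The missing reference rate adds a smaller problem. Any reaction to the first infusion, even Grade 1, closes the 30-minute option. But a patient who reacts at Grade 2 on 30 minutes is slowed, on the natural reading, to a rate that is still faster than the one already given without reaction.

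What is at stake is patient protection in later cycles. Infusion-related reaction is one of the two adverse events of special interest in Section 11.11, and a worse reaction ends treatment.

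**Working it through.** Table 2 states no duration, so there is no figure of the plan's own to reproduce.

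**Inputs.** First infusion 90 ± 10 minutes and optional later infusion 30 ± 5 minutes (Sections 5.1 and 8.1.2); rate cut 50% (Table 2).

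**Step 1: the two rules applied to one event.** Take a Grade 2 reaction that recurs at an uncut rate despite pre-medication.

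| Next infusion | First rule | Second rule, read literally |
|---|---|---|
| Same rate, pre-medication only | Compliant | Not compliant |
| Half rate, no pre-medication | Compliant | Not compliant |
| Half rate and pre-medication | Compliant | Compliant |

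The first row is the regimen that failed. Two sequences show it:

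- Cycle 1 at 90 minutes, no reaction; Cycle 2 at 30 minutes, Grade 2; Cycle 3 at 30 minutes with pre-medication, Grade 2; Cycle 4 at 30 minutes with pre-medication. Cycle 4 meets the first rule.
- Cycle 1 at 90 minutes, Grade 2; Cycle 2 at 90 minutes with pre-medication, Grade 2; Cycle 3 at 90 minutes with pre-medication. Cycle 3 meets the first rule.

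The second rule's last sentence follows a sentence about patients whose rate was cut and then restored. If it is confined to them, only the first rule governs these sequences and the failed regimen may continue. If it is read more widely, the two rules give different answers. The text needs correcting either way.

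**Step 2: what half the rate means after a reaction at 30 minutes.** At fixed dose and volume, halving the rate doubles the duration: 2 × 30 = 60 minutes, with window 2 × 25 = 50 to 2 × 35 = 70. Compared with the first infusion, the rate ratio is 90/60 = 1.5, from 80/70 = 1.14 to 100/50 = 2.0. The slowed infusion is therefore faster than the first one across the whole window.

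**Step 3: time cost of going no faster than 90 minutes.**

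- Against the 60-minute step: 90 − 60 = 30 minutes more (80 − 70 = 10 to 100 − 50 = 50).
- Against staying at 30 minutes: 90 − 30 = 60 minutes more (80 − 35 = 45 to 100 − 25 = 75).
- After recurrence at 90 minutes despite pre-medication: 2 × 90 = 180 minutes in total (160 to 200).

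**Step 4: reach into the analyses.** Section 10.7.3 updates the dose-escalation model from Cycle 1 DLT data. Cycle 1 has one infusion, given over 90 minutes. A reaction can recur only at a second infusion, so neither rule operates inside the DLT window. The efficacy definitions in Section 10.5.2 do not use infusion rate.

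**The case against.** The strongest reply is that judgment already covers most of this. The 30-minute option is never compulsory, so an investigator may go back to 90 minutes after a first reaction. Section 6 provides for expert consultation and contact with the Medical Monitor, and Section 3.3 lists adverse event and physician decision as reasons to stop. A Grade 2 reaction, as Table 2 defines it, settles quickly with symptomatic care. All of that stands and keeps the point small. It does not repair an obligation that the failed regimen can satisfy.

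Two stronger readings are tempting, and the documents do not support them.

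- *A reader might infer that half rate could mean 60 or 180 minutes after a reaction at 30, a threefold spread between sites.* The Synopsis does attach the word initial to the first infusion ("If there is no infusion-related reaction after the initial 90-minute infusion on Cycle 1 Day 1"), but there it describes an infusion, not a rate. In Table 2 the 50% cut first appears for restarting an interrupted infusion, where it naturally means half the running rate, and the later lines refer back to it. Getting from 30 to 180 minutes would be a cut to one sixth of the rate. For a reaction at 90 minutes the terms are clear. Sections 5.1 and 8.1.2 also send administration details to the Pharmacy Manual, which is not among the documents and may define the rates. Calling the 30-minute option a reduced rate is loose, but the duration stands beside it.
- *A reader might infer that nothing covers recurrence at half rate with pre-medication.* The first rule does apply there; it lets the regimen continue unchanged. A compulsory stop, or a compulsory 180 minutes for everyone who reacts, would be a clinical preference and not the repair of an omission.

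**Conclusion.** The point holds as a minor patient-safety correction. The *and/or* in the first rule lets a failed regimen continue and does not match the second rule. This applies to a recurrence at 30 or at 90 minutes. The rate point is narrower: it concerns only patients moved to 30 minutes who then have a Grade 2 reaction, for whom the natural reading gives about 60 minutes (50 to 70), 1.5 times faster (1.14 to 2.0) than the infusion given without reaction.

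The conclusion rests on equal dose and volume across infusions, and on taking the 50% from the running rate. The number of patients affected is unknown because the documents give no reaction rate. Nor do they show that rate causes later-cycle reactions or that 90 minutes would stay tolerated, so the benefit is plausible but unmeasured. The dose-escalation model and the efficacy analyses are unaffected. Section 5.1.3 lets the final MTD draw on "an overall assessment of safety data from subsequent cycles", so later reactions could enter that judgment, but the link is remote and adds nothing to the severity.

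**What to change.** Amend only the rate lines of the Grade 2 entry in Table 2.

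1. In the rule for recurrence despite pre-medication, replace *and/or* with *and*.
2. State that the 50% cut is taken from the rate at which the reaction occurred.
3. State that after a Grade 2 reaction at 30 minutes, whether during or after the infusion, later infusions go no faster than the 90 ± 10 minute infusion. This limit also applies to the return step. A restart within the same infusion stays at half the running rate.

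The text on interruption, symptomatic treatment and pre-medication can stay as it is.

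The cost is one short amendment and longer chair time: about 30 to 60 more minutes per infusion for a patient who reacted at 30 minutes, and about 180 minutes in total only for a patient whose reaction recurs at 90 minutes despite pre-medication. No new procedure or data field is needed, since Section 7.6 already requires infusion start and end times on the eCRF.

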### 3.2 Exclusion Criteria

Patients who meet any of the following criteria will be excluded from study entry:

1. Treatment with any of the following:
  - History of an allogeneic bone marrow or solid organ transplant within 3 months before the start of study treatment
  - Concomitant treatment with any medication that is classified as having a known or possible risk of Torsades de pointes should be avoided from the start of study treatment through the end of Cycle 3 (see [www.crediblemeds.org](http://www.crediblemeds.org) and [Appendix E](#)). Consult with Medical Monitor if such medication is needed during the study.
  - Prophylactic administration of G-CSF, filgrastim, pegfilgrastim, erythropoietin, or the transfusion of blood, red blood cells (RBC), or platelets within 14 days before the start of treatment and during Cycle 1. Chronic therapy with erythropoietin at stable dose that started at least  $> 14$  days before the first dose of DS-6157a may continue.

2. Has unresolved toxicities from previous anticancer therapy, defined as toxicities (other than alopecia) not yet resolved to NCI CTCAE version 5.0, Grade  $\leq$ 1.

Patients with chronic Grade 2 toxicities may be eligible following discussion with the Medical Monitor.

3. Has spinal cord compression or clinically active CNS metastases (including brain metastases), defined as untreated and symptomatic, or requiring therapy with steroids or anticonvulsants to control associated symptoms. Patients with treated brain metastases that are no longer symptomatic and who require no treatment with steroids may be included in the study if they have recovered from the acute toxic effect of radiotherapy.
4. Has known hypersensitivity to either the drug substances or inactive ingredients in the drug product.
5. Has a prior or concurrent malignancy whose natural history or treatment has the potential to interfere with the safety, efficacy, or any other assessments of the investigational regimen based on consultation with the Medical Monitor.
6. Has a documented history of myocardial infarction or unstable angina within 6 months before study treatment.
7. Has a medical history of symptomatic congestive heart failure (New York Heart Association classes II–IV; [Appendix D](#)) or a serious cardiac arrhythmia requiring treatment.
8. Has a corrected QT by Fridericia's formula (QTcF), of  $>470$  ms based on the average of triplicate 12-lead electrocardiogram (ECG) per local read.

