- Patient who meets any of exclusion criteria based on the most recent data, or who experienced ILD of any grade or any other dose modification toxicity event during DS-6157a treatment will not be eligible for IPDE.

IPDE may be conducted up to a dose that is 1 dose level below the dose already established to be safe and tolerable. Dose escalation should not be more than 3 dose levels at a time. The actual dose level will be decided based on the overall individual clinical status and PK profile. A patient may be allowed further IPDE after completing a minimum of another 4 cycles after the first IPDE, as long as the conditions for IPDE are met. AEs arising after IPDE should follow dose modifications/reductions per [Table 2](#), but further re-escalations will be prohibited after such events.

Dose can be delayed for up to 28 days from the planned date of administration. If a patient has a persisting AE/SAE that requires a longer dose delay, then patient will be withdrawn from the study after consulting with Medical Monitor.

Treatment cycles for a patient for whom DS-6157a dosing was temporarily withheld for any reason may have future cycles scheduled based on the date of the last DS-6157a dose. However, the tumor assessments will follow the pre-specified schedules relative to the start of the study treatment (Cycle 1 Day 1).

Investigators may contact the Medical Monitor or designee to discuss questions regarding dose modification or discontinuation of study drug.

All confirmed or suspected coronavirus disease 2019 (COVID-19) infection events must be recorded in the eCRF. Please refer to [Appendix H](#) for additional information on dose modifications.

*CONFIDENTIAL*

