LVEF 40% to 45% and decrease is 10% - 20% (absolute value) from baseline	Interrupt DS-6157a dosing Repeat LVEF assessment within 3 weeks If LVEF has not recovered to within 10% (absolute value) from baseline, discontinue patient from study treatment. If LVEF recovers to within 10% from baseline, resume treatment with study drug.
LVEF <40% or >20% (absolute value) drop from baseline	Permanently discontinue from study treatment
Electrocardiogram QT prolonged	
Grade 3 (Average QTcF >500 ms or >60 ms change from baseline)	Repeat the ECG in triplicate within 1 hour and then monitor at the frequency determined by the Investigator's discretion. Delay dose until resolved to ≤ Grade 1 (QTcF ≤480 ms or change from baseline ≤30 msec), determine if another medication the patient was taking may be responsible and can be adjusted or if there are any changes in serum electrolytes that can be corrected, then if attributed to DS-6157a and confirmed on repeat ECG triplicate, reduce dose 1 level.
Grade 4 (Torsade de pointes or polymorphic ventricular tachycardia or signs/symptoms of serious arrhythmia)	Discontinue patient from study treatment
Interstitial lung disease (ILD)/pneumonitis	If a patient develops radiologic changes potentially consistent with ILD/pneumonitis or an acute onset of new or worsening pulmonary function or other related signs/symptoms such as dyspnea, cough, or fever, rule out ILD/pneumonitis.  If the AE is confirmed to have an etiology other than ILD/pneumonitis, follow the management guidance outlined in the "Other Non-Laboratory Adverse Events" dose modification section below.  If the AE is suspected to be ILD/pneumonitis, treatment with study drug should be interrupted pending further evaluations.

CONFIDENTIAL

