#### 7.5 ECG Measurements

For each set of triplicate ECGs, three standard resting 12-lead ECGs will be obtained not more than 3 minutes apart each from the previous ECG. ECGs will be obtained after the patient has been resting quietly in semi-supine or supine position for at least 5 minutes before the first ECG and during the triplicate. When ECG and PK assessments coincide, ECGs must be done **within** 10 minutes **before** the scheduled PK sample. When ECG and blood draws other than PK coincide, ECGs should be done before these blood draws, however these blood draws (other than PK) may be taken more than 10 minutes after ECGs, or ECGs may be done more than 10 minutes after these blood draws (other than PK). ECG parameters to be recorded are: Heart rate; RR, PR, and QT intervals; QRS duration; ECG body position; interpretation of ECG. Depending on the emerging ECG data during dose escalation, ECGs may be transmitted to a central reading vendor, as an option.

Triplicate ECG measurements will be collected at the following time points:

*CONFIDENTIAL*

- Screening
- Cycle 1 Day 1: Pre-dose and after end of infusion (EOI), and 2, 4, and 7 hours ( $\pm 15$  minutes) after EOI
- Cycle 1 Day 2: 24 hours ( $\pm 2$  hours) after the start of Day 1 infusion
- Cycle 1 Days 4, 8, and 15 ( $\pm 1$  day)
- Cycle 1 Day 22: only in patients with planned PK assessment
- Cycle 2 Day 1: Pre-dose and after EOI
- Cycle 2 Days 8 and 15 ( $\pm 2$  days)
- Cycle 2 Day 22: only in patients with planned PK assessment
- Cycle 3 Day 1: Pre-dose and after EOI, and 2, 4, and 7 hours ( $\pm 15$  minutes) after EOI
- Cycle 3 Day 2: 24 hours ( $\pm 2$  hours) after the start of Day 1 infusion
- Cycle 3 Days 4 ( $\pm 1$  day), 8 and 15 ( $\pm 2$  days)
- Cycle 3 Day 22: Pre-dose (only in patients with planned PK assessment)
- Cycle 4 and beyond: Pre-dose on Day 1

A single ECG will be obtained at the EOT visit.

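### The QT row of Table 2 can end the dose delay while the patient is still Grade 3, for any baseline QTcF below 420 ms

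*Combined protocol and SAP*

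**What the plan says.** The row on QT prolongation in Table 2 (Section 6) sets the trigger as "Grade 3 (Average QTcF >500 ms or >60 ms change from baseline"). Either limb is sufficient.

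The row then asks for a repeat triplicate ECG within 1 hour and further monitoring at a frequency the investigator chooses. Dosing is delayed until the event has "resolved to ≤ Grade 1 (QTcF ≤480 ms or change from baseline ≤30 msec"). The row also asks for a check of other medication and serum electrolytes, "then if attributed to DS-6157a and confirmed on repeat ECG triplicate, reduce dose 1 level".

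Related text:

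- Exclusion criterion 8 (Section 3.2) bars a QTcF above 470 "ms based on the average of triplicate 12-lead electrocardiogram (ECG) per local read". There is no lower limit.
- Section 6 states that "All dose modifications must be based on the worst preceding toxicity".
- Section 6 also states: "Dose can be delayed for up to 28 days from the planned date of administration". A longer delay leads to withdrawal after consulting the Medical Monitor.
- Section 7.5 schedules triplicate ECGs before dosing on Day 1 of Cycles 1, 2 and 3, and then "Cycle 4 and beyond: Pre-dose on Day 1". There is thus an ECG before every dose.

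**The concern.** The trigger treats a rise from baseline as a QT signal in its own right, whatever the absolute value. The release criterion does not carry that through: a patient delayed for a large rise can be released on the absolute limb alone. If baseline is low enough, that limb was already met when the event was graded, so the delay has no length.

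Read literally, a patient in a first-in-human study could be redosed while still Grade 3 by the same row. The one-level reduction is only a partial safeguard, because it requires attribution to DS-6157a and confirmation on a repeat triplicate. If another drug or an electrolyte disturbance is held responsible, the literal text allows redosing at the same dose with the rise still above 60 ms.

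**Working it through.** Let *B* be baseline QTcF and *Q* the average QTcF at an assessment, both in ms. The plan gives no figure of its own here; the check is of threshold logic.

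**Inputs**

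- Grade 3 (Table 2): *Q* > 500 or *Q* − *B* > 60.
- Release (Table 2): *Q* ≤ 480 or *Q* − *B* ≤ 30.
- Eligible at entry (exclusion criterion 8): *B* ≤ 470.

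**Can one reading be both Grade 3 and released?** There are four combinations of limbs.

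1. *Q* > 500 with *Q* ≤ 480: impossible.
2. *Q* − *B* > 60 with *Q* − *B* ≤ 30: impossible.
3. *Q* > 500 with *Q* − *B* ≤ 30: needs *B* ≥ *Q* − 30 > 470, which criterion 8 excludes at entry.
4. *Q* − *B* > 60 with *Q* ≤ 480: needs *B* + 60 < *Q* ≤ 480. This has a solution exactly when *B* < 480 − 60 = 420, and the window is 420 − *B* wide.

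| Baseline | Both Grade 3 and released | Width | Largest rise accepted as resolved | What the ≤30 ms limb would require |
|---|---|---|---|---|
| 380 | 441–480 | 40 | 480 − 380 = 100 | ≤410 |
| 400 | 461–480 | 20 | 480 − 400 = 80 | ≤430 |
| 410 | 471–480 | 10 | 480 − 410 = 70 | ≤440 |
| 415 | 476–480 | 5 | 480 − 415 = 65 | ≤445 |
| 420 or more | none | 0 | – | – |

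For example, baseline 400 and QTcF 465 is a rise of 65 ms, which is Grade 3; 465 is also below 480, which is release.

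A count in whole ms, with baselines 340–470 (the lower end is an assumption) and QTcF 340–600, agrees. Every baseline from 340 to 419 has at least one such reading and none from 420 to 470 has any. The total is 1 + 2 + … + 80 = 3,240 baseline–reading pairs, all from combination 4.

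**Does a repair close the gap?**

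- *Both limbs required (joined by and)*: *Q* ≤ 480 rules out *Q* > 500, and *Q* − *B* ≤ 30 rules out *Q* − *B* > 60. No overlap remains.
- *Each limb paired with its trigger*: a delay triggered only by *Q* > 500 has a rise of at most 60, so *B* > 440. Release at *Q* ≤ 480 then leaves a rise below 480 − 440 = 40, which is not Grade 3. A delay triggered only by the rise has *B* + 60 < *Q* ≤ 500, so *B* < 440. Release at *Q* ≤ *B* + 30 is then below 470, which is not Grade 3. If both triggered, both limbs apply. No overlap remains, even when the release ECG is later than the trigger ECG.
- *Difference between the two repairs*: they differ only when the absolute limb alone triggered (whole-ms baselines of 441 or more) and *B* + 30 < 480. That is baselines 441–449, and the largest gap is 480 − (441 + 30) = 9 ms.

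**The case against.** The strongest reply is that the overlap appears only if the parenthesis is read apart from the words it explains. The instruction is to wait for Grade 1 or better, and the same row says a rise above 60 ms is Grade 3, so such a patient has not resolved. The trigger and release limbs are also printed in the same order with the same connector, so pairing is the natural reading and may well be what was meant. This has force as to intent. But the parenthesis is the row's only definition of the release grade, its limbs are joined by *or*, and nothing says they correspond to the triggers. At best the row contradicts itself. The worst-preceding-toxicity rule does not help: it selects the row, not the end of the delay.

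A second reply is that compact *or* phrasing is the table's style; the creatinine row uses it in both its trigger and its release. The LVEF row for values of 40% to 45% with a 10–20% fall shows that the table can tie resumption to change: "If LVEF recovers to within 10% from baseline, resume treatment with study drug". That comparison is imperfect, because its trigger limbs are joined by *and*. The case does not depend on it.

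Third, the consequence is narrow. It needs a baseline below 420 ms, a rise above 60 ms with QTcF no higher than 480 ms, persistence at a pre-dose ECG, and a site that follows the lenient reading. QT-risk drugs are to be avoided through Cycle 3, sites may contact the Medical Monitor, and safety signals are reviewed at least monthly. All of this stands and limits the severity. None of it requires the rise to fall before redosing.

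Finally, criterion 8 applies at entry, whereas Section 10.2 takes baseline as the last value before the first dose. A Day 1 baseline above 470 ms is therefore not clearly excluded, and combination 3 in the working could then occur. This is a secondary boundary and does not affect the main overlap. Pairing the limbs covers it too, since release after *Q* > 500 would require *Q* ≤ 480.

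**Conclusion.** The concern holds. As written, the QT row lets one average QTcF be both Grade 3 and sufficient to end the delay for every baseline below 420 ms, over a window 420 minus baseline wide. The 420 ms limit follows exactly from the row's own thresholds. That no overlap exists at 420 ms or above assumes that baseline does not exceed 470 ms.

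The effect is confined to the delay and matters for dosing only if the reading is present at a pre-dose ECG. How many patients would be affected cannot be estimated, because no baseline QTcF distribution is given, and how sites would read the row is not known. This is a defect in a cardiac safety rule that should be corrected; it does not undermine the study.

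**What to change.** Replace the parenthesis in the QT row with paired release limbs, using triplicate averages for both baseline and post-dose values:

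- delay triggered by average QTcF above 500 ms: release at average QTcF of 480 ms or less;
- delay triggered by a rise above 60 ms: release at a rise of 30 ms or less;
- both triggered: both required.

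Joining the two existing release limbs with *and* is a shorter alternative that also removes the overlap. For eligible baselines it is stricter than pairing only at 441–449 ms, by at most 9 ms.

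The cost is wording in one table row. No assessments are added, because pre-dose triplicates are already scheduled. The downside is longer delays for some patients: at baseline 380 ms, for example, QTcF must return to 410 ms or less. A delay beyond the 28-day limit means withdrawal after consulting the Medical Monitor. The documents do not allow that cost to be sized.
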